6. STUDY DESIGN

This is a prospective nonrandomized study in patients undergoing laparoscopic surgery for endometriosis.

7. STUDY SIZE

The study will enroll 20 patients.

8. DURATION

The total duration of the study is expected to be approximately four months. Two months to enroll and two months to complete last follow-up visit and study report.

9. STUDY ENDPOINTS

To answer the research question posed the following data will be collected:

1. The ability to complete the procedure without increasing pneumoperitoneum due to visualization.
Any increase beyond 10mm Hg and the reason for change will be recorded.
2. The quality of visualization in the laparoscopic field of view will be assessed by the investigator using a Visual Analog Scale (VAS).
3. Patient satisfaction with cosmesis outcome at the discharge follow-up visit assessed by means of a survey scaled from “very unsatisfied” to “very satisfied.”
4. Post-Surgery Pain assessment based upon a Numerical Rating Scale (NRS) where 0 is “no pain at all” to 10 “worst pain imaginable” and the location of the pain using a body diagram.
5. Pain medication utilization

10. OTHER DATA COLLECTION

- End tidal CO₂ volume (etCO₂) (taken at the start of the procedure and at the completion of the procedure),
- Adverse Events,
- Electrosurgical instrument(s) used,
- Preoperative assessment: patient demographics, medical history, medication information, height and weight, pain (at intake visit)
- Number of endometriosis lesions resected

11. SUBJECT IDENTIFICATION & SELECTION

Potential subjects will be identified from the clinical practice of the participating investigator or by their respective research staff. Patients presenting to the clinical practice of the participating investigator for diagnosis or treatment consistent with the inclusion criteria will be informed about the study.

With referral from the treating physician/provider, patients scheduled for surgery prior to the start of the study may be contacted via telephone by a study team member to inform them of the study, assess their interest and assess their eligibility to participate. An IRB approved script will be used for such calls. For interested patients, a copy of the informed consent can be mailed or emailed to the patient for their review and consideration prior to their next clinic visit or the scheduled procedure.

Each new subject presenting for evaluation or inclusion is to be assessed for adherence to the following inclusion/exclusion criteria. Determination of whether subjects satisfy the criteria may be established by review of medical records, subject interview, physical examination, or testing as appropriate. A baseline form is used to collect subject screening information and baseline assessments. Patients are considered enrolled once it has been demonstrated that the inclusion/exclusion criteria have been met and the patient signs the informed consent.

The study allows for an intraoperative exclusion for excessive abdominal wall thickness or other anatomical characteristics that prevent the use of Ultravision. If this should occur, the patient will be withdrawn from the study. The withdrawal will be recorded on the withdrawal case report form. The patient will be replaced.

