4. DEVICE DESCRIPTION

The Ultravision™ System is an accessory to electrosurgical instruments that is used to clear the surgical smoke generated during their use and as such will only be used when such devices are in use. An example of the effect of the Ultravision™ System during use to improve the visualization of the field of view is demonstrated in Figure 2 below:

[figure not shown]

Figure 1. View before and during cutting with an electrosurgical instrument

Figure 2. Electrosurgical smoke without (left hand image) and with (right hand image) Ultravision.

The system includes the following elements:

Standalone battery-operated generator unit

Figure 3. Ultravision Generator with battery pack

Ionwand™, which is introduced into the abdomen of the patient through either the Ultravision™ 5mm Trocar or a 2.5mm percutaneous catheter and provides the source of the electrons that create the negative ions that transiently charge the surgical smoke particles.

Figure 4. Ionwand, sterile assembly in package (top), 5mm Trocar (bottom)

Other accessories include a patient return adaptor and battery recharging station.

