11.2. EXCLUSION CRITERIA

Subjects MUST not have any of the following:

E1	Existing comorbidities that would contraindicate them for laparoscopic surgery.
E2	Patient anatomy that is not compatible with the use of the Ionwand catheter i.e. abdominal wall thickness that exceeds the working length of the Ionwand catheter identified intraoperatively
E3	Patient with a BMI >50
E4	Be pregnant

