18. ADVERSE EVENTS

18.1. ADVERSE EVENT CATEGORIES

For purposes of this protocol the adverse event definitions are derived from GCP standards and FDA Guidance.⁸

Table 4
Adverse Event Definitions

Adverse Event (AE)	Untoward medical occurrence, unintended disease or injury, or untoward clinical signs (including abnormal laboratory findings) in subjects, users or other persons, whether or not related to the medical device. Includes events related to the study device or comparator device, or the procedures involved.
Serious Adverse Event (SAE)	
Adverse event that:
 
▪ Led to death▪ Led to serious deterioration in the health of the subject, that:
○ Resulted in a life-threatening illness or injury, or○ Resulted in a permanent impairment of a body structure or a body function, or○ Required in-patient hospitalization or prolongation of existing hospitalization, or○ Resulted in medical or surgical intervention to prevent life-threatening illness or injury or permanent impairment to a body structure or a body function○ Led to fetal distress, fetal death, or a congenital abnormality or birth defect 
Planned hospitalization for a pre-existing condition without serious deterioration in health, is not considered a serious adverse event. Hospitalization is defined as an admission greater than 24 hours

Adverse Device Effect (ADE)	Untoward and unintended response to a medical device or as a consequence of inadequate labeling and includes any event that is a result of user error.
Serious Adverse Device Effect (SADE)	Untoward medical occurrence that happens in a subject or other person, is related to the study device, comparator, or procedure, and is serious, but is not unanticipated

⁸ Clinical Investigation of Medical Devices for Human Subjects - Part 1: General Requirements. ISO 14155-1. International Organization for Standardization. 2011.

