19. PATIENT WITHDRAWAL

A patient may choose to withdraw from participation in the study at any time without penalty. If a patient chooses to withdraw, they will still receive medical care consistent with the standard of care. The investigator may at their discretion withdraw a patient from participation or where intraoperative exclusions (defined in the I/E criteria) occur. Other examples include if the procedure necessitates conversion from laparoscopic to open technique, lack of adherence to visit schedule, adverse events, or safety concerns. For all withdrawals the date, point in the study, and reason for withdrawal will be recorded. Patients that withdraw prior to the procedure or are withdrawn from the study due to an intraoperative exclusion are replaced.

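### Patients excluded during surgery for incompatible anatomy are withdrawn and replaced, with no statement that post-operative adverse event follow-up continues after an attempted insertion

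*Protocol*

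**What the plan says.** Section 11 sets the rule: "The study allows for an intraoperative exclusion for excessive abdominal wall thickness or other anatomical characteristics that prevent the use of Ultravision". It continues: "If this should occur, the patient will be withdrawn from the study". The only form named is the withdrawal form: "The withdrawal will be recorded on the withdrawal case report form". Section 19 confirms replacement: "Patients that withdraw prior to the procedure or are withdrawn from the study due to an intraoperative exclusion are replaced". For every withdrawal it requires the date, the point in the study and the reason, and nothing more.

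Exclusion criterion E2 in Section 11.2 describes the typical case: "abdominal wall thickness that exceeds the working length of the Ionwand catheter identified intraoperatively". Section 4 says that the Ionwand enters the abdomen through "either the Ultravision™ 5mm Trocar or a 2.5mm percutaneous catheter".

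On safety data, Table 4 in Section 18.1 defines adverse events broadly: "Includes events related to the study device or comparator device, or the procedures involved". The text below the table requires every adverse event to be recorded on an Adverse Event Form. Table 3 in Section 15 lists intraoperative adverse events, and has device malfunction recorded as one. After surgery, the Study Data Collection Schedule in Section 32 places adverse event assessments at discharge, at the 14-day visit and at unscheduled visits. Section 17 describes the 2-week visit as current standard of care.

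**The concern.** E2 can be met only after consent and once the operation has begun. A wall thicker than the catheter's working length may be recognised because an insertion was tried and did not reach. Such a patient has been exposed to part of the device procedure, yet leaves the study at that moment and is replaced by someone in whom the device could be used.

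A harm that appears later, for example at the puncture site, would surface at discharge or by 2 weeks. Those are the assessments that no longer apply to a withdrawn patient. Adverse events belong to the fifth study objective, and Section 25.2 sets the results beside other studies and the literature. With 20 patients, one uncollected event changes the reported rate visibly, and the loss can only make the device look safer.

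**Working it through.** **Reading the sections together**

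1. *When exclusion happens.* Section 11 and E2 place it during surgery. Neither says whether an insertion has been attempted by then. The route of entry in Section 4 makes an attempt possible, not certain.
2. *What is recorded at exclusion.* Section 11 names the withdrawal form. Section 19 asks for date, point and reason.
3. *What is still recorded for events during the operation.* Section 15 (Table 3) and Section 18.1 require intraoperative events, device malfunctions and adverse events of any kind to be recorded. Neither exempts a patient who is then withdrawn, so a harm seen at the attempt is covered.
4. *What is recorded afterwards.* The discharge, 2-week and unscheduled-visit assessments are study assessments. No sentence in Sections 11, 17 or 19, or in the schedule, continues them after withdrawal. The care promised in Section 19 is standard medical care for patients who choose to withdraw, not study data collection.
5. *Who is owed study records.* Section 12 says enrolment occurs once all participation criteria are met, and Section 30.1 requires completed case report forms for each enrolled subject. A site could read a patient who fails E2 on the table as never enrolled, which adds to the doubt.

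**Size**

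The plan gives no figure to reproduce. The sample size is set by judgement ("The study will enroll 20 patients"), without an error rate, power or expected exclusion rate.

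Inputs: 20 retained patients (Section 7), and k = number excluded after an attempted insertion, which the protocol does not give and which is assumed here to be 1 to 3.

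Share of exposed patients with no stated post-operative study safety follow-up = k / (20 + k):

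| k (assumed) | Share |
|---|---|
| 1 | 1/21 = 4.8% |
| 2 | 2/22 = 9.1% |
| 3 | 3/23 = 13.0% |

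Hypothetical effect on the reported rate, with k = 3, one delayed harm among those three and none among the 20 retained:

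- Excluded patients neither followed nor counted: 0/20 = 0% (exact 95% upper limit 16.8%).
- Excluded patients followed and counted: 1/23 = 4.3% (exact 95% interval 0.1% to 21.9%).

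**The case against.** A reader might infer that harms from a failed placement vanish from the adverse event data. The documents do not support that: an injury seen during the attempt is recordable under Sections 15 and 18.1, and Section 18.3 sends serious events to the review board with no exception for withdrawn patients. Nor does the withdrawal rule contradict the adverse event definition, which says what counts as an event and sets no follow-up period or analysis population. The trigger is anatomy that prevents use of the device, not every difficult or failed placement. No timing of replacement is given. Exposure before exclusion is possible but not stated. All of this stands, and it confines the point to delayed harms and to counting.

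It can also be said that little is at stake. Section 25.1 says that this post-market study of a cleared device is not meant to demonstrate safety and efficacy, adverse events sit under other data collection in Section 10, analysis is descriptive, and the intervals for 0/20 and 1/23 overlap almost entirely. That limits the weight of the point but does not remove it: the study still plans to report adverse events.

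A statistical analysis plan could define the safety population and the table layout. It could not recover data from assessments that the protocol has ended, so follow-up after withdrawal has to be settled in the protocol.

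Finally, Section 19 also allows withdrawal for conversion to open surgery, adverse events or safety concerns, and is equally silent on follow-up there. That is fair, and it argues for a slightly wider sentence rather than none.

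**Conclusion.** The point holds as a gap in safety follow-up. Applied as written, Sections 11 and 19 take a consented and possibly exposed patient out of the study before any post-operative adverse event assessment, and do not say whether that patient is counted in the adverse event summary. It does not show that harms have been or will be lost, and intraoperative events should be captured under the present text.

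The affected share is 4.8% to 13.0% of exposed patients if 1 to 3 exclusions follow an attempted insertion. Both the number and the assumption that each exclusion came after an attempt are mine; if every exclusion came before insertion, the share would be zero. The contrast between 0% and 4.3% rests on a single hypothetical delayed event. This is a worthwhile, inexpensive correction and does not threaten the study's main purpose. How these exclusions affect the feasibility denominator is a separate matter.

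**What to change.** Add a sentence to each of Sections 11 and 19: any patient in whom insertion of the Ionwand, its trocar or its catheter was started remains in the study for adverse event collection at discharge, at the 2-week visit and at any unscheduled visit, even if replaced for the other endpoints. State also that these patients are counted in the adverse event summary, with their number and reasons for exclusion reported. The withdrawal form should record whether insertion had been started, so that exclusions before and after an attempt can be told apart. The Section 19 sentence could cover other investigator-initiated withdrawals after the device has been used at no further cost. A patient's own right to withdraw is unaffected.

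The cost is a few extra case report forms and one extra line in the adverse event summary. These patients have already consented, and the 2-week visit is standard of care. The downside is a possibly less favourable adverse event rate. Nothing in the clinical conduct of the procedure changes.

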11.1. INCLUSION CRITERIA

Subjects MUST meet all the following:

I1	Is 18 years or older.
I2	Provide written informed consent prior to trial procedures after studies indicate that the patient needs the prescribed procedure.
I3	Agrees to attend all follow-up assessments.
I4	Is indicated for laparoscopic surgery for the treatment of endometriosis.
I5	Able to read and understand English

11.2. EXCLUSION CRITERIA

Subjects MUST not have any of the following:

E1	Existing comorbidities that would contraindicate them for laparoscopic surgery.
E2	Patient anatomy that is not compatible with the use of the Ionwand catheter i.e. abdominal wall thickness that exceeds the working length of the Ionwand catheter identified intraoperatively
E3	Patient with a BMI >50
E4	Be pregnant

12. SUBJECT INFORMED CONSENT

A partial waiver of HIPAA Authorization is being requested for the purposes of initial screening for study eligibility and recruitment purposes. Identifiable health information to be accessed under this waiver will include contact information, demographics, and medical history. Only study team members will have access to this information. Safeguards to maintain privacy and confidentiality of information will be taken as described in the data collection and management section of the protocol. Patient inclusion could be substantially hindered without the ability to review patients' records for eligibility and recruitment purposes, particularly for patients who may have already been scheduled for surgery at the time the study begins.

Referred patients presenting for diagnosis or treatment consistent with the inclusion/exclusion criteria will undergo the informed consent process to authorize the gathering of data recorded on the Subject Screening & Enrollment Form. The study investigator will administer informed consent or may delegate the responsibility to a qualified individual as long as it is defined on the study responsibility log. When administering consent, it must be evident that the participant comprehends the nature of the study and the risks and benefits. Evidence is the patient is able to verbalize these topics in sufficient detail to confirm comprehension.

Completion of the informed consent does not constitute enrollment. Enrollment occurs once screening is complete and all criteria for participation have been met.

Subjects must document their consent for study participation by signing the Institutional Review Board approved Informed Consent Form. The informed consent process must be consistent with the Declaration of Helsinki. The subject must be given the opportunity to ask questions of, and receive answers from, study personnel prior to a request to sign the Informed Consent Form. This form is to be co-signed by the investigator. Failure to obtain consent prior to subject participation is considered a protocol deviation and must be reported to the Institutional Review Board.

Note that subjects will be asked to provide consent so that data related to their eligibility status data can be gathered.

After the subject and investigator sign the Informed Consent Form, the original is to be filed in the subject's study binder. Copies will be filed in the subject's medical record and the subject is also to be given a copy.

13. SCREENING & ENROLLMENT

Patient demographics and other baseline information will be collected to establish whether the patient meets the requirements for the study. It is assumed that a physical exam will be conducted as part of the standard of care. Only limited information on the patient's health status is collected for the study as defined in Table 1 below. Each patient will be assigned a unique study number. Baseline information will be collected, consistent with the standard of care. Baseline assessment is conducted at the preoperative visit.

Table 1
Baseline Assessment – Conducted at Pre-op visit

Type of Information	Data Sources	Time Frame
Date of Evaluation	Investigator Report	NA
Subject Age	Subject interview / Medical Record	NA
Height	Medical Record	NA
Weight	Medical Record	NA
Body Mass Index (BMI)	Medical Record	
Prior/Existing Medical Conditions	Subject interview & medical record	Within three months prior to surgery
Prior/Existing Medical Interventions	Subject interview & medical record	Within three months prior to surgery
Diagnosis Indicating Surgical Intervention	Investigator Report	Within three months prior to surgery
Current Pain Medications and Reason for Taking	Subject interview & medical record	Within three months prior to surgery

14. PREOPERATIVE PROTOCOL

Patients will be assessed preoperatively in accordance with the current standard of care.

Table 2
Pre-Surgery (Intake) Assessment

Type of Information	Data Sources
Date of Evaluation	Investigator Report
Completed Informed Consent	Investigator Report
Changes since baseline assessment	Medical Record/Patient Report
• Medical conditions • Pain Medications • Medical interventions/Adverse Events	
Pregnancy Test	Medical Record
Pain Assessment	Subject Report

Table 2
Pre-Surgery (Intake) Assessment

Type of Information	Data Sources
Pain Medications	Subject Report

15. PROCEDURE PROTOCOL

The device is used in accordance with the instructions for use. An initial target pneumoperitoneal pressure setting of 10mmHg will be used for the procedure. At the discretion of the surgeon investigator, pressure will be adjusted as needed to accomplish the surgical procedure. A standard insufflator with 3mm ports and one 5 mm ports will be used for the procedure.

Table 3
Intraoperative/Procedure Information

Type of Information	Time Point	Data Sources
Date of Procedure	Before opening	Patient Medical Record
Pneumoperitoneum pressure after camera trocar is inserted	Intraoperative	Investigator Report
Increase in pressure and reason for change	Intraoperative	Investigator Report
Adverse Events	Intraoperative	Investigator Report
Unplanned concomitant interventions or procedures	Intraoperative	Investigator Report
End tidal volume of CO ₂ (etCO ₂), recorded at the beginning and end of the procedure.	Intraoperative	Investigator Report
Number of CO ₂ liters consumed	At completion of the procedure	Investigator Report
Surgeon Survey on Quality of Visualization and Smoke Management	Immediately Post-operative	Investigator Report
Ultravision device(s) used (lot# and model #)	Immediately Post-operative	Investigator Report
Diathermy device(s) used	Immediately Post-operative	Investigator Report
Device Malfunction – recorded as an adverse event	Intraoperative	Investigator Report
Number of Endometriosis Lesions Resected	Post-operative	Operative Report / Investigator Report
Pain Assessment	Just Prior to discharge	Medical Record

Table 3
Intraoperative/Procedure Information

Type of Information	Time Point	Data Sources
Pain Medications	Prescribed at discharge	Medical Record

16. SURGEON SURVEY

Immediately post procedure the investigator will be asked to provide feedback regarding visibility and smoke management during the procedure. Responses will be recorded on a VAS scale.

1. Overall quality of visualization.
2. How often was smoke management a negative factor during the procedure.

17. POST PROCEDURE FOLLOW-UP PROTOCOL

16.1 Post-operative days 1-7:

Subjects will be asked to complete a daily diary/self-assessment of pain. The assessment will include a pain rating, location of pain and medications taken for pain. The diary/self-assessment is included as a separate document.

16.2 Post-operative 2 week (\pm 3 days) follow up visit:

A 2 week follow up visit is current standard of care. At this visit, adverse events will be assessed. A final pain assessment will be administered during this visit.

16.3 Post-operative 4 week (\pm 1 week) follow up phone call:

Patient satisfaction with cosmesis (scar appearance) after the surgery will be collected by means of a telephone follow-up where a simple cosmesis satisfaction survey will be administered by a study team member.⁷

16.5 Unscheduled visit:

⁷ Steinemann D, Raptis D, Lurje, Oberkofler C, Wyss R, Zehnder A, Lesurtel M, Vonlanthen R, Clavien P, Breitenstein S. Cosmesis and body image after single-[prt la paroscopic or conventional la paroscopic cholecystectomy: a multicenter double blinded randomized controlled trial (SPOCC-trial), BMC Surg. 2011; 11:24, September 2011.

A pain assessment and adverse event assessment will be performed at any unscheduled visit.

Additional evaluations will be completed at the discretion of the Principal Investigator based on the subject's presenting complaint.

